# **1.0 INTRODUCTION AND RATIONALE**

Glaucoma is a collection of disorders characterized by progressive loss of visual fields due to optic nerve damage, and is the leading cause of blindness in the U.S., affecting 1-2% of individuals aged 60 and over. Research has determined that the rate of primary open-angle glaucoma (POAG) – the most common form of glaucoma -- in the United States is at 2.2 million people. Based on that figure, it is estimated that between three and six million people in Europe, and approximately 3 million people in South America have elevated intraocular pressure and are at an increased risk for developing POAG. POAG accounts for 90% of all cases of glaucoma. It is a slow, progressive disease that produces no symptoms in its early stages. Although the drainage system of the eye remains open and functions properly, the eye is unable to remove the excess fluid at a pace sufficient to prevent a rise in intraocular pressure (IOP). Progressive vision loss tends to be painless, and subjects often present with advanced disease.

Although there are many risk factors associated with the development of glaucoma (age, race, myopia, family history, and injury), elevated intraocular pressure is the only risk factor that can be successfully treated and that is correlated with the reduction of glaucomatous optic neuropathy. Management of glaucoma requires chronic, lifelong treatment with a spectrum of therapeutic options including medications, laser treatment and microsurgical devices / implants, all with the therapeutic goal of lowering intraocular pressure to target levels in order to prevent loss of visual fields from excessive pressure on the optic nerve.

Historically, first-line treatment for elevated intraocular pressure consists of medical therapy. Results of the Early Manifest Glaucoma Trial (EMGT), the Advanced Glaucoma Intervention Study (AGIS), the Collaborative Initial Glaucoma Treatment Study (CIGTS), the Normal Tension Glaucoma Study (NTG), and the Ocular Hypertension Treatment Study (OHTS) indicate that topical ocular hypotensive medication is effective in reducing intraocular pressure and thus delaying or preventing the progression of POAG.

Several major pharmacologic classes of therapeutic agents are used in the treatment of glaucoma. The mechanism of action consists of either decreasing aqueous fluid production in the ciliary epithelium, improving aqueous outflow via the trabecular meshwork (responsible for 80% of normal outflow) or the uveoscleral route (20%), or a combination of these methods.

While currently available glaucoma medications are generally effective, these drugs are not without side effects. Approximately 5% to 15% of subjects on prostaglandin analogues experience ocular side effects such as hypertrichosis, iris pigmentation, conjunctival hyperemia, and darkening of the periocular skin. These side effects may serve to further discourage subjects from adhering to the dosing regimen. Close to 60% of latanoprost monotherapy subjects experienced adverse events, at a rate of 1.7 events per subject, and 20% of subjects who discontinue latanoprost within first 24 months of treatment cite adverse events as the reason for discontinuation. This rate increased to 1.9 with addition of a beta-blocker and to 2.4 with brimonidine plus a beta-blocker. Adverse events associated with glaucoma medications included toxicity, allergic response, bronchospasm, cardiac failure, depression, impotence.

In the face of the complexity of therapeutic regimens, the chronic use of multiple medications, the need for frequent daily administration, the presence of side effects and the chronic asymptomatic nature of POAG, subjects often do not take their medication consistently. This presents the physician with a significant problem of subject non-compliance.

In a comprehensive review of 76 studies published between 1986-2000, mean drug compliance was found to be approximately 71% (S.D. 17%, range 34%-97%) and declined as the number of daily doses increased. Approximately 12% of glaucoma patients on once or twice daily dosing regimens reported missing a significant number of doses. Patients often underestimate their level of defaulting when questioned. In a study using a pilocarpine eye drop monitor, on average, patients administered 76% of their eye drops, but reported taking 97% of the required dosage. Patients often take their medication as prescribed on the day of a visit to the doctor, but when asked, admit to not taking their medication on a regular basis. A study examining compliance with timolol found that non-complaint patients went a mean of 85 days per year without medication, with a maximum of 165 days.

The ability to administer eye drops, particularly in the elderly, and understanding of the disease and treatment are also important factors. Brown et al (1984) found that even in patients experienced in the use of topical eye drops, 13% were unable to instill topical medications into both eyes successfully despite multiple attempts. Therefore, when combining all of the factors that can affect proper administration of glaucoma medication, the adherence to therapy factor is only 60.5% (79% prescription refilled, drops are instilled correctly 87% of the time, and patients administer the medication in a timely fashion 88% of the time).

Finally, it is known that long-term topical therapy engenders local conditions which may adversely affect the outcome of possible future filtration surgery. Because glaucoma requires lifelong management, there is a concern that prolonged use of medications may ultimately reduce sight saving therapeutic options.

These limitations of glaucoma medications, and the need for continuous long-term follow-up in order to prevent glaucoma progression of glaucoma and potential vision loss, have led to interest in the use of glaucoma implants. Since open-angle glaucoma and cataracts are present with increasing frequency in older patients, and these conditions co-exist in an estimated 20% of cataract surgery patients (CMS published data), the ability to implant a glaucoma device during scheduled cataract surgery offers a unique opportunity for concurrent placement of a glaucoma implant without the risk of an additional intraocular surgical procedure. Implantation of a glaucoma device designed to provide additional lowering of IOP can mitigate issues of drug compliance in elderly glaucoma patients with the continuous treatment offered by an implant. An example of one such implant that has been CE marked and licensed (#80214) in Canada is the *iStent*® Trabecular Micro-Bypass Stent (Glaukos Corporation, Laguna Hills, CA. Model GTS 100L/R). The operating principle of this device is to provide a conduit for aqueous humor through the trabecular meshwork, thereby increasing aqueous flow.

Ivantis has developed the *HydrusTM Aqueous Implant* for the purpose of decreasing IOP. The Hydrus provides a conduit through the trabecular meshwork and also scaffolds Schlemm's canal, the aqueous collector channel that surrounds the eye. The implanted Hydrus serves to both maintain or dilate Schlemm's canal and provide an opening through the trabecular meshwork to restore the natural outflow pathway of the eye. This dual function may improve IOP reduction compared to the *iStent*.

On 26 May 2011, the *HydrusTM Aqueous Implant* was granted CE Mark by the National Standards of Authority of Ireland (CE 0050) for the reduction of IOP in POAG subjects.

# Figure 2: Hydrus implanted within Schlemm's Canal

# Figure 3: The Hydrus Implant Procedure

Nitinol, a nearly equal part composition of nickel (Ni) and titanium (Ti), is one of a very few alloys that is both highly elastic and biocompatible. Nitinol, which is formed by alloying nickel and titanium (~ 50% Ni), is a shape memory alloy with super elastic properties very similar to those of bone in comparison to the highly limited elasticity of stainless steel, another commonly used biomaterial. Nitinol's super elastic properties also allow delivery of an implant through very tortuous / restrictive passages with minimal force. More importantly, the device will still retain its intended geometry while other metals would be deformed to unintended geometries. These properties make nitinol an especially advantageous material for biomedical applications. Some of the biomedical applications that utilize nitinol include stents, heart valve tools, bone anchors, staples, septal defect devices and implants. It should be noted that nitinol's self-expanding property, or a return to its desired geometry by means of temperature change, a difference between room temperature and body temperature, are not utilized by the Hydrus.

# 3.0 STUDY OBJECTIVE

The objective of this clinical trial is to compare the effectiveness of the *HydrusTM Implant* to the *iStent* for lowering intraocular pressure (IOP) in glaucoma subjects undergoing cataract removal and intraocular lens implantation.

# 4.0 STUDY DESIGN

This study is a post-market prospective, randomized, controlled, multicenter clinical trial in which a total of approximately 150 subjects will be randomized after successful cataract surgery to receive either the *Hydrus Implant* or the *iStent*. Potential study participants will be consented, at which time they will undergo screening criteria for eligibility. If eligibility criteria are met after initial screening, the study participants will undergo a screening washout phase during which all glaucoma medications (topical and oral) will be discontinued; the duration of the washout phase to be determined by the specific medication(s) used by the subjects. Following washout, the subjects will return for a baseline evaluation, and if found to continue to meet the eligibility requirements, and agree to participate, will be scheduled for cataract surgery, randomized, and followed up at specified intervals for a 2 year period. The study schema is presented in Figure 4.

Of the two eye implants being used in this study, the *HydrusTM Aqueous Implant* (the test article) is currently CE marked for use in the EU countries. It is intended for the reduction of intraocular pressure (IOP) in subjects with primary open angle glaucoma (POAG), pseudoexfoliative glaucoma, or pigmentary glaucoma as a stand-alone treatment or in conjunction with cataract surgery. The *iStent* (the control article) is currently CE marked for use in the EU countries. It is intended for the reduction of IOP in POAG subjects with concurrent cataract or in stand-alone treatment, and is thus considered a suitable control.

In the event a study subject does not respond to device therapy, hypotensive glaucoma medications may need to be prescribed during the follow up period to reduce IOP to a safe level, at the discretion of the attending physician. To address the confounding effect of medications on the assessment of the devices' ability to reduce IOP, a "wash-out" of all glaucoma medications will be conducted prior to the 12 and 24 month follow-up visits.

Figure 4: Study Schema

# 5.0 STUDY ENDPOINTS

The primary effectiveness endpoint for this study is diurnal IOP at 12 months following the washout of all glaucoma medications.

Secondary effectiveness endpoints include:

- A reduction in IOP of at least 20% following the wash-out, as compared to the washed-out baseline.
- An IOP of no less than 5mmHg and no more than 18mmHg at 12 months post washout.

Safety outcomes include loss of lines of BCVA, results of slit lamp and fundus examination, and the incidence of complications and adverse events.

#### 6.0 STATISTICAL METHODS

#### 6.1 Study Hypothesis

Previous clinical research has shown that the risk for glaucomatous progression is significantly reduced when IOP is lowered,

#### 6.2 Sample Size

The study size is based on the primary endpoint.

A power calculation yields a sample size of 65 subjects per arm for a 1:1 randomization ratio. Assuming a 15% loss to follow up at 12 months, a total of 75 randomized subjects are required per arm.

#### 6.3 Safety Analysis

All study subjects randomized in the study will be evaluated for safety outcomes. Frequency tabulations of safety outcomes will be performed at 1, 3, 6, 12, 18 and 24 months

# 7.0 STUDY POPULATION

#### 7.1 Inclusion Criteria

Male and female subjects who meet the inclusion and exclusion criteria in this protocol, will be eligible for enrollment in this study. *Ocular criteria relates to the study eye only*.

- Male and female subjects, from 21 to 84 years of age.
- A diagnosis of primary open angle glaucoma (POAG), pseudoexfoliative glaucoma (PXG), or pigmentary dispersion glaucoma (PDG).
- An operable age-related cataract with BCVA of 20/40 or worse, eligible for phacoemulsification.

# 7.3 Exclusion Criteria

Excluded from the study will be individuals with the following characteristics. Unless specified otherwise, all ocular criteria refer to the study eye only.

- Closed angle forms of glaucoma
- Diagnosis of acute angle closure, traumatic, congenital, malignant, uveitis, or neovascular glaucoma.
- Secondary (such as neovascular, uveitic, traumatic, steroid induced, lens induced, or glaucoma associated with increased episcleral venuous pressure), congenital, or developmental glaucoma.
- Previous argon laser trabeculoplasty (ALT). Selective laser trabeculoplasty (SLT) is allowed

#### 8.0 STUDY PROCEDURES

#### 8.1 Subject Entry, Consent and Enrollment

Participants will be recruited from the Investigators' subject population or referrals. Subjects that appear to be eligible subjects will be approached for study participation and sign a subject informed consent (PIC) prior to the commencement of study related procedures. The investigator or designee will explain the study purpose, procedures, and subject responsibilities to the potential participant. The subject shall be given the opportunity to ask questions and allowed time to consider the information provided. The subject's willingness and ability to meet the follow-up requirements will be determined. When the subject agrees to participate, written informed consent will be obtained, at which time the subject will undergo eligibility requirements, to determine possible enrollment into the study. One copy of the informed consent form will be retained with the subject's medical records, and one copy will be provided to the subject.

Study-specific initial screening tests will then be performed and if all initial screening criteria are met, the subject will be considered enrolled in the study. Approximately 100 subjects will be enrolled in the study; approximately 30% are expected to drop out due to pre- or intra-operative entry criteria, resulting in a 70 subject randomized population.

Only one qualified eye per qualified subject may be randomized for treatment. If both eyes qualify for enrollment, the eye with the worse best corrected visual acuity (BCVA) will be designated as the study eye. If the qualifying visual acuity is obtained using the BAT meter, the eye with the worse BCVA will be designated as the study eye. If a subject's study eye fails to qualify for surgery, the subject's fellow eye may be considered for enrollment after the IOP in the study eye is considered to meet the eligibility requirements.

After the subject has successfully completed the preoperative screening exam, he or she will be instructed to discontinue any ocular hypotensive medications in the designated treatment eye for the appropriate washout period, as listed in Table 2, *prior to* the Baseline Exam. If upon washout, the subject experiences an IOP spike of > 36 mmHg, or requires the reintroduction of hypotensive medications due to an IOP spike, or a surgical intervention during the preoperative period, the subject will be treated and will be considered for withdrawal from the study. However, sites should confirm with Ivantis if there are any questions.

TABLE 2         OCULAR HYPOTENSIVE MEDICATION WASHOUT PERIODS							
Carbonic Anhydrase Inhibitors							
Diamox ® (Acetazolamide) − oral Rx	14 days						
Neptazane® (Methazolamide) – oral Rx	14 days						
Azopt ® (Brinzolamide)	14 days						
Trusopt ® (Dorzolamide Hydrochloride)	14 days						
Alpha Adrenergic Agonist							
Alphagan ® (Brimonidine)	14 days						
Iopidine ® (Apraclonidine Hydrochloride)	14 days						
Beta Blockers							
Betagan ® (Levobunolol Hydrochloride)	28 days						
Betoptic ® (Betaxalol Hydrochloride)	28 days						
OptiPranolol® (Metipranolol)	28 days						
Timoptic/Betimol ® (Timolol Maleate)	28 days						
Prostaglandin Analogs							
Lumigan ® (Bimatoprost)	28 days						
Travatan ® (Travoprost)	28 days						
Xalatan ® (Latanoprost)	28 days						

TABLE 2 (Cont'd)         OCULAR HYPOTENSIVE MEDICATION WASHOUT PERIODS							
Combined Medications							
Combigan ® (Brimonidine Tartrate/Timolol Maleate)	28 days						
Cosopt ® (Dorzolamide Hydrochloride/ Timolol Maleate)	28 days						
Pilocarpine	7 days						
Dipivefrin and epinephrine products 28 days							

If subjects have not used any ocular hypotensive medications, they may be scheduled for a Baseline Visit up to 45 days after successfully completing the Screening Visit. At the Baseline Visit, upon confirmation of a successful washout, subjects will undergo an evaluation for continued eligibility.

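### Section 8.1 plans for 70 randomised subjects, while Sections 4.0 and 6.2 require about 150; a trial run to 8.1 would have about 30 evaluable per arm instead of 65

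*Combined protocol and SAP*

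**What the plan says.** Three sections of the combined protocol and SAP give the trial's size.

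- **Section 4.0 (Study Design):** "a total of approximately 150 subjects will be randomized after successful cataract surgery".
- **Section 6.2 (Sample Size):** "A power calculation yields a sample size of 65 subjects per arm for a 1:1 randomization ratio". It continues: "Assuming a 15% loss to follow up at 12 months, a total of 75 randomized subjects are required per arm". Two arms of 75 make 150, so this agrees with Section 4.0.
- **Section 8.1 (Subject Entry, Consent and Enrollment):** "Approximately 100 subjects will be enrolled in the study". The section then allows for a loss of some 30% of these "due to pre- or intra-operative entry criteria, resulting in a 70 subject randomized population".

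Section 8.1 also fixes what enrolment means: "if all initial screening criteria are met, the subject will be considered enrolled in the study". Enrolment therefore comes before washout, the baseline visit and surgery, and the 30% is attrition before randomisation. The 15% in Section 6.2 is loss after randomisation. Section 8.1 allows one study eye per subject, so eyes and subjects are the same count. Section 8.9 says that terminated subjects are not replaced.

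**The concern.** The number randomised is stated as 150 in one place and 70 in another, a factor of 2.1, and both statements are current text. Section 8.1 is the only part of the available text that gives an enrolment number, and it is the section on subject entry. Sites, ethics committees and whoever prepares the site-level randomisation lists could reasonably plan from it.

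The available text has no rule for when accrual ends that would show which figure governs. If accrual stopped near 70, the protocol could be cited in support, yet the primary comparison of two active devices would have less than half of the evaluable sample that Section 6.2 says it needs. If accrual ran to 150, Section 8.1 would be exceeded by 80 subjects.

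A smaller matter sits in Section 6.2. The step from 65 evaluable to 75 randomised per arm does not quite cover the stated 15% loss.

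**Working it through.** **Inputs.** 65 evaluable per arm, 1:1 allocation, 15% loss by 12 months and 75 randomised per arm (Section 6.2); about 150 randomised (Section 4.0); about 100 enrolled, about 30% attrition before randomisation and 70 randomised (Section 8.1).

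**1. Reproducing the stated figures**
- Section 8.1: 100 x (1 - 0.30) = 70. It is internally correct.
- Sections 4.0 and 6.2: 2 x 75 = 150. They agree with each other.
- Section 6.2, step from 65 to 75: 65 x 1.15 = 74.75, which rounds up to 75.
- The 65 per arm itself cannot be reproduced, because the available text gives no significance level, power, difference or SD.

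**2. Can the two totals be reconciled?**
- 70 per arm: this would be 140 randomised, which 100 enrolled cannot supply.
- 70 per site: Section 8.1 speaks of the whole study.
- Rounding: the word approximately cannot cover 70 against 150.
- Different populations: both figures count randomised subjects.

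**3. Sample delivered under Section 8.1**
- Randomised per arm: 70 / 2 = 35.
- Evaluable per arm after 15% loss: 35 x 0.85 = 29.75, about 30.
- Share of requirement: 29.75 / 65 = 46%. Randomised: 70 / 150 = 47%.

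**4. Enrolment needed for 150 randomised at 30% attrition**
- 150 / 0.70 = 214.3, so about 215, against the stated 100.

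**5. Effect on precision and power**
- Ratio of confidence-interval widths at the same SD: sqrt(65 / 29.75) = 1.48. This needs no assumption about design power.
- Power depends on assumptions, since the design values do not appear. Taking a two-sample t-test at the 5% level, I solved for the standardised difference that gives the assumed power at 65 per arm, then recomputed power at 29.75 per arm:

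| Assumed design at 65 per arm | Implied difference (SD units) | Power at 29.75 per arm |
|---|---|---|
| two-sided, 80% | 0.495 | 46.7% |
| two-sided, 90% | 0.573 | 58.4% |
| one-sided, 80% | 0.439 | 51% |
| one-sided, 90% | 0.516 | 63% |

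**6. The smaller slip in Section 6.2**
- To keep 65 after 15% loss: 65 / 0.85 = 76.5, so 77 per arm.
- 75 per arm keeps 75 x 0.85 = 63.75.
- The loss that 75 per arm can bear while keeping 65: 1 - 65/75 = 13.3%.
- Cost, under the same two-sided assumption: 80% falls to 79.2%, and 90% to 89.4%.

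**The case against.** The strongest reply is that Section 8.1 states a study-wide expectation and does not instruct sites to stop at 100 enrolled or 70 randomised. Two sections agree on 150, and Section 6.2 is the only one that derives its number, so a reader might treat it as governing and the 70 as a leftover. That is a fair description of the wording, and it makes the 30-per-arm outcome conditional on Section 8.1 being followed. It does not remove the conflict. The documents do not say that the smaller figures are superseded, and an explanation for an error does not correct it.

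A second reply is that the power figures are hypothetical. This stands: they depend on the assumed design power and on a one- or two-sided test, and across the cases shown they run from about 47% to 63%. The 46% share of the required sample and the 1.48 width ratio do not depend on those choices.

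Third, the 75-versus-77 point is close to a rounding convention and costs under one percentage point of power. That also stands; the seriousness of the finding does not rest on it.

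Last, the 30% attrition comes from the same sentence as the disputed 100 and 70, and the sponsor may have intended 70. So 215 is only as reliable as the 30%, and the sponsor should confirm both the target and the rate. If planning really did follow Section 8.1, the practical cost would also exceed a text edit.

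**Conclusion.** The concern holds and must be fixed. A sample size on which the trial relies is stated in two incompatible ways, and no reading of the text reconciles them. If Section 8.1 were followed, the primary endpoint would be analysed on about 30 evaluable subjects per arm instead of 65, with an interval about 1.48 times as wide. On the assumption of a two-sided 5% test designed for 80% to 90% power, power would be about 47% to 58%; one-sided, about 51% to 63%. These results apply Section 6.2's 15% loss to Section 8.1's 70 randomised, which is appropriate because the two losses occur at different stages. The shortfall in Section 6.2, 63.75 against 65 evaluable per arm, is real but minor.

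**What to change.** - **Section 8.1:** replace the enrolment and randomisation figures with ones that agree with Sections 4.0 and 6.2, namely about 215 enrolled for about 150 randomised at 30% attrition. Confirm that 30% is still the expected rate; if it changes, enrolment is 150 divided by (1 - the rate).
- **Section 6.2:** keep 75 per arm and restate the expected evaluable number as about 63 to 64 per arm, or equivalently state the tolerated loss as 13.3%. Moving to 77 per arm (154 in total, 154 / 0.70 = 220 enrolled) is possible but not necessary.
- **If 70 randomised is what the sponsor intends:** revise Sections 4.0 and 6.2 instead, with a power statement for about 30 evaluable per arm.

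The target should be settled in writing before outcome data could influence it. With 150 retained, the change to the document is wording in Sections 8.1 and 6.2, and the randomised size already stated does not move. If recruitment was in fact planned on 100 enrolled, the recruitment plan has to be more than doubled as well.
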